### **Relationship to study drug**

For all AEs, the investigator will assess the causal relationship between the study drug and the AE using his/her clinical expertise and judgment according to the following algorithm that best fits the circumstances of the AE:

#### Unrelated

- May or may not follow a reasonable temporal sequence from administration of the study product

- Is biologically implausible and does not follow known response pattern to the suspect study drug (if response pattern is previously known).
- Can be explained by the known characteristics of the subject's clinical state or other modes of therapy administered to the subject.
- Unlikely
- May or may not follow a reasonable temporal sequence from administration of the study product
- Is biologically not very plausible
- May be explained by the known characteristics of the subject's clinical state or other modes of therapy administered to the subject.

#### Possible related

- Follows a reasonable temporal sequence form administration of the study drug.
- May follow a known response pattern to the study drug (if response pattern is previously known).
- Could not be reasonably explained by the known characteristics of the subject's clinical state or other modes of therapy administered to the subject, if applicable.
- Probable
- Follows a reasonable temporal sequence form administration of the study drug.
- Follows a known response pattern to the study drug (if response pattern is previously known).
- other causes for the event are unlikely

#### Definitely related

- Follows a reasonable temporal sequence form administration of the study drug.
- Follows a known response pattern to the study drug (if response pattern is previously known).
- No other reasonable cause is present.

### **Reporting procedures**

A special section is designated to adverse events in the case report form. The following details must thereby be entered:

- Type of adverse event
- Start (date and time)
- End (date and time)
- Severity (mild, moderate, severe)

- Serious (no / yes)
- Unexpected (no / yes)
- Outcome (resolved, ongoing, ongoing – improved, ongoing – worsening)
- Relation to study drug (unrelated, possibly related, definitely related)

Adverse events are to be documented in the case report form in accordance with the above mentioned criteria.

### Reporting procedures for SAEs

In the event of serious, the investigator has to use all supportive measures for best patient treatment. A written report is also to be prepared and made available to the clinical investigator immediately. The following details should at least be available:

- Patient initials and number
- Patient: date of birth, sex, ethical origin
- The suspected investigational medical product (IMP)
- The adverse event assessed as serious
- Short description of the event and outcome

If applicable, the initial report should be followed by the Follow up report, indicating the outcome of the SAE.

All SAEs for which there is a reasonable possibility the experience may have been caused by clazakizumab (this applies to both expected and unexpected events) will be recorded on a CIOMS Form and submitted to:

SAE Reporting	Contact Information
Vitaeris Drug Safety: [name] This must be reported to Vitaeris within 24 hours.	[contact] (Office), [name] (cell) email: [contact] For submission of SAE report information: By email: [contact] or [contact]

### Reporting procedures for SUSARs

It must be remembered that the regulatory authorities, and in case of SUSARs which could possibly concern the safety of the study participants, also the Institutional Review Board / Independent Ethics Committee (IRB / IEC) are to be informed. Such reports shall be made by the study management and the following details should be at least available:

- Patient initials and number
- Patient: date of birth, sex, ethical origin
- Name of investigator and investigating site
- Period of administration
- The suspected investigational medical product (IMP)
- The adverse event assessed as serious and unexpected, and for which there is a reasonable suspected causal relationship to the IMP
- Concomitant disease and medication
- Short description of the event:
  - Description
  - Onset and if applicable, end
  - Therapeutic intervention
  - Causal relationship
  - Hospitalization or prolongation of hospitalization
  - Death, life-threatening, persistent or significant disability or incapacity

Electronic reporting should be the expected method for reporting of SUSARs to the competent authority.

### **The Development Safety Update Report (DSUR)**

The DSUR will be provided by the principal investigator at least once a year.

This report will also be presented annually to the Independent Ethics (IEC) and to the competent authorities by the sponsor.

## **11. STUDY TERMINATION, WITHDRAWAL AND REPLACEMENT OF SUBJECTS**

### *Criteria for withdrawal*

Subjects may prematurely discontinue from the study at any time. Premature discontinuation from the study is to be understood when the subject did not undergo EOS examination and / or all pivotal assessments during the study.

Subjects will be withdrawn under the following circumstances:

- at their own request
- if the investigator feels it would not be in the best interest of the subject to continue

- if the subject violates conditions laid out in the consent form / information sheet or disregards instructions by the study personal

In all cases, the reason why subjects are withdrawn will be recorded in detail in the CRF and in the subject's medical records. Should the study be discontinued prematurely, all study materials (complete, partially completed and empty CRFs) will be retained.

#### *Follow-up of patients withdrawn from the study*

In case of premature discontinuation after study drug intake, the investigations scheduled for the EOS visit will be performed 7 days after study drug discontinuation. The subjects will be advised that participation in these investigations is voluntary. Furthermore, they may request that from the time point of withdrawal no more data will be recorded and that all biological samples collected in the course of the study will be destroyed.

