The pleiotropic pro-inflammatory cytokine interleukin-6 (IL-6), which is known to play a pivotal role not only as a trigger of acute phase responses, but also in the activation and development of B cells and antibody production, may be a promising target for ABMR treatment. Monoclonal antibodies against IL-6 and the IL-6 receptor (IL-6R) have been proven to be effective in the treatment of various autoimmune diseases, including rheumatoid arthritis (RA). More recently, targeting IL-6/IL-6 receptor has gained interest also in the context of organ transplantation. In a recent uncontrolled trial by Choi et al. the anti-IL6R monoclonal antibody tocilizumab was evaluated as treatment of chronic ABMR unresponsive to IVIg, rituximab and/or plasmapheresis in a cohort of 36 kidney transplant recipients. The results of this uncontrolled trial are promising, showing a beneficial safety profile, a reduction

in DSA levels, and stabilization of kidney function at 2 years. A major result of this study was a marked reduction in the extent of microcirculation inflammation in follow-up biopsies. The authors noted graft losses in four recipients in whom tocilizumab was prematurely stopped. For these cases, a role of a rebound effect by accumulated IL-6.

Direct binding and blockade of IL-6 may be an attractive alternative. Clazakizumab (formerly ALD518, BMS945429), is a high affinity humanized monoclonal antibody which binds to IL-6 and prevents interaction and signaling via IL-6R. This antibody is the most potent and longest acting agent in the IL-6/IL-6R blocking category, is free of antibody-dependent cellular cytotoxicity (ADCC) and complement-dependent cytotoxicity (CDC) and does not crosslink any surface receptors. Its half-life is about 30 days [subcutaneous (SC) administration], and monthly SC injections allow for sustained IL-6 blockade. Its safety has so far been established in more than 800 subjects, many of them treated within phase 2 studies performed in RA or psoriatic arthritis (PsA).

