**Clinical Pharmacology.** Following the administration of clazakizumab as a 1-hour IV infusion, the PK of clazakizumab were linear over the dose ranges of 30 mg to 640 mg in healthy subjects and 80 mg to 320 mg in subjects with RA as indicated by consistent clearance at these dose levels. The T-half of clazakizumab at all doses was very similar in healthy male subjects and in subjects with RA and was consistent with that expected for a humanized IgG1 antibody. Across the doses studied, the mean T-half of clazakizumab ranged from 19.5 to 31.0 days in healthy male subjects and from 26.4 to 30.9 days in subjects with RA. The T-half of clazakizumab after SC administration in healthy male subjects was similar to the IV administration. In a Phase 1 study comparing IV and SC dosing in healthy male subjects, the mean T-half of clazakizumab was 30.7 days after a single IV dose and 31.1 to 33.6 days after SC administration. The bioavailability of clazakizumab after SC administration was 60% of the IV formulation. As expected, Cmax was lower and Tmax was longer for the SC administration relative to IV administration. Population PK analysis of the data from clinical studies in RA, PsA and healthy subjects have indicated that body weight affects the PK of clazakizumab such that both clearance and central volume of distribution increase with increasing body weight. Therefore, heavier subjects will have lower drug exposure compared with less heavy subjects.

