Primary outcome measures are the safety and tolerability of clazakizumab, evaluated throughout the study period (19 visits until EOS visit at 52 weeks). Secondary endpoints are pharmacokinetics (clazakizumab concentration) and pharmacodynamics (suppression of CRP). For preliminary efficacy assessment, blood-derived biomarkers of ABMR (HLA/DSA antibody levels, cytokines and markers of endothelial injury, patterns of peripheral blood leukocyte subpopulations) and IL-6/IL-6R gene expression will be assessed at day 0, and after 12 and 52 weeks. The study will include two protocol biopsies, an early biopsy after 11 weeks (end of part A) to primarily dissect the effect of IL-6 blockade on microcirculation inflammation in direct comparison to placebo, and a late biopsy after 51 weeks to assess the

effect of clazakizumab on the progression of chronic injury (cg score, IFTA score). All biopsies will in addition be evaluated for ABMR-typical gene expression patterns (ATAGC, Alberta University, Edmonton; major read-out: molecular ABMR score). We will in addition monitor kidney function, protein excretion and graft survival over the whole study period. Finally, we will assess the impact of IL-6 blockade (as compared to placebo) on pharmacokinetics of pantoprazole reflecting CYP-dependent liver metabolism. At day 0, week 12 and week 52, pantoprazole will be administered at a dosage of 20 mg intravenously, and drug levels will be determined every hour over a period of 6 hours. In patients on continuous proton pump inhibitor therapy, oral treatment will be paused for 3 days before pharmacokinetic testing, and re-started one day thereafter.

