### ***Drug Interaction***

The formation of CYP450 enzymes may be suppressed by increased levels of cytokines (eg, IL-6) during chronic inflammation. Therefore, it is expected that for molecules that antagonize cytokine activity, such as clazakizumab, the formation of CYP450 enzymes could be normalized. When starting or stopping therapy with clazakizumab, patients taking medications which are individually dose-adjusted and metabolized via CYP450, 3A4, 1A2, or 2C9 (e.g. atorvastatin, calcium channel blockers, theophylline, warfarin, phenytoin, cyclosporine, or benzodiazepines) should be monitored as doses may need to be adjusted to maintain their therapeutic effect. Given its long elimination half-life ( $t_{1/2}$ ), the effect of clazakizumab on CYP450 enzyme activity may persist for several weeks after stopping therapy.

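### Section 11 does not separate stopping study drug from leaving the study, and the only follow-up it describes is a voluntary visit 7 days after the drug stops

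*Combined protocol and SAP*

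**What the plan says.** Section 11 defines premature discontinuation as discontinuation from the study, recognised by a missing EOS examination and/or missing pivotal assessments. Besides the patient's own request, it gives two grounds for withdrawal: "if the investigator feels it would not be in the best interest of the subject to continue" and "if the subject violates conditions laid out in the consent form / information sheet or disregards instructions by the study personal". It has no category for a patient who stops the drug but stays under observation.

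The next paragraph, on follow-up of withdrawn patients, is timed from the drug and not from leaving the study: "the investigations scheduled for the EOS visit will be performed 7 days after study drug discontinuation". Patients are told that these investigations are voluntary, and "they may request that from the time point of withdrawal no more data will be recorded". No later visit is described.

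Section 9 contains rules that stop clazakizumab only: after GI perforation, with malignancy, after anaphylaxis or serious hypersensitivity, and at the laboratory limits in Tables 6 to 8. None says whether the patient then stays on the visit schedule.

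Other sections assume full follow-up. In Section 5, safety and tolerability are "evaluated throughout the study period (19 visits until EOS visit at 52 weeks", graft survival is monitored for the entire study, and graft and patient survival at one year is a secondary outcome. Section 7 states intention-to-treat analysis and uses Kaplan-Meier and log-rank methods for graft, patient and AE-free survival.

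**The concern.** Intention-to-treat analysis needs outcomes after the drug is stopped, and the primary outcome is safety to week 52. If a centre applies the Section 11 paragraph as written, a patient withdrawn on the investigator's judgement or for non-adherence has one more voluntary visit and then no described follow-up. The event that led to the stop is already recorded. What can be lost is later, different events, week 52 measurements (week 12 as well for early stops) and one-year graft and patient status.

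These patients are unlikely to be a random subset, because a best-interest withdrawal may well relate to prognosis. Censoring them in the Kaplan-Meier analyses is then potentially informative.

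The protocol's own background gives reason to observe them. Section 1 says of the uncontrolled tocilizumab trial: "The authors noted graft losses in four recipients in whom tocilizumab was prematurely stopped". It then mentions a rebound effect, in a sentence that is incomplete in the available text. Section 9 adds that "the effect of clazakizumab on CYP450 enzyme activity may persist for several weeks after stopping therapy". The wording also allows the two centres to handle the same drug stop differently.

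**Working it through.** The plan gives no figure for early stopping, so there is none to reproduce. The check has three parts: timing, drug remaining and number affected.

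**1. Timing.** Inputs from Table 3: doses at weeks 0, 4, 8, ..., 48 (13 doses); visits at weeks 0, 1, 2, 3, 4, 8, 11, 12, 16, 20, 24, 28, 32, 36, 40, 44, 48, 51 and 52 (19 visits). A patient dosed at week 48 has had every planned dose, so premature stops are those with a last dose at weeks 0 to 44, which is 12 points. Section 11 does not define the date of drug discontinuation under 4-weekly dosing, so both readings are shown.

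| Dating | Final visit | Weeks lost | Mean lost (even spread, assumption) | Final visit before week 11 |
|---|---|---|---|---|
| Last dose week + 1 | weeks 1, 5, 9, ..., 45 | 51 down to 7 | (51 + 7)/2 = 29 | 3 of 12 |
| Next due dose week + 1 | weeks 5, 9, ..., 49 | 47 down to 3 | (47 + 3)/2 = 25 | 2 of 12 |

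Dated from the last dose, the final visit comes at 1/52 = 2% to 45/52 = 87% of the 52 weeks. After week 1, 17 of the 19 scheduled visits remain; after week 45, 3 remain (weeks 48, 51 and 52). The week 11 biopsy is missed wherever the final visit falls before week 11. The second biopsy is less clear: Table 3 puts it at week 51, outside the EOS column, but the Part B description in Section 3 links it to the EOS visit. Whether the 7-day investigations include a biopsy cannot be settled from the text.

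**2. Drug remaining at the final visit.** Input from Section 1: a half-life of "31.1 to 33.6 days after SC administration". Fraction remaining = 0.5^(days / half-life), assuming first-order decline from the last dose and ignoring absorption.

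- 7 days after the last dose: 0.5^(7/31.1) = 0.856 and 0.5^(7/33.6) = 0.866, about 86%.
- 7 days after the next due dose (28 + 7 = 35 days): 0.5^(35/31.1) = 0.458 and 0.5^(35/33.6) = 0.486, or 46-49%.
- Completers for comparison (week 48 to week 52, 28 days): 0.536 to 0.561, or 54-56%.

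None of this applies to Part A placebo patients.

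**3. Number affected.** The plan states none. Three sources within the documents give a range if carried over to this trial (assumption):

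- Table 5, AE discontinuation on 25 mg in arthritis: 2.4% of 41 is 1 patient and 0% of 59 is 0, so 1/100 = 1% (exact 95% CI 0.03-5.4%). 20 x 0.01 = 0.2 patients (up to 1.1).
- Section 1, tocilizumab cohort: at least 4 of 36 stopped early, 11.1% (exact 95% CI 3.1-26.1%). 20 x 0.111 = 2.2 patients (0.6-5.2). This is a different drug, with 2-year results.
- Table 4, earlier late-ABMR trial, missing one-year values: 0/44 for protein/creatinine ratio, 1/44 = 2.3% for eGFR and 5/44 = 11.4% for DSA. Times 20: 0, 0.5 and 2.3 patients. Reasons are not given, and these are missing values, not drug stops.

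Together this suggests about 0 to 3 of 20, with an upper limit of about 5. Each patient is 1/20 = 5% of the cohort and 1/10 = 10% of a Part A arm.

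**The case against.** The strongest reply is that the harm depends on a reading the text does not require. A drug stop is not among the grounds for withdrawal in Section 11, and the Section 9 rules stop the drug only, so such a patient could naturally be taken to stay on Table 3. The right to ask that no more data be recorded also implies that recording could otherwise continue. This stands to the extent that a reader might infer from Section 11 that every patient who stops drug leaves the study after 7 days, and the documents do not say so. It does not remove the point: no section requires visits after a drug stop, and investigator-decided withdrawals fall under Section 11 on any reading.

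A withdrawal clause is also an exception to a schedule, and Kaplan-Meier methods accept incomplete follow-up. That is fair, and the problem is better called a poor fit than a contradiction. Potentially informative censoring remains. Patients who withdraw consent cannot be followed under any design.

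A reader might also infer that the 7-day visit always falls while most of the drug is present and before a rebound could be seen. Neither is supported in general. Dated from the next due dose, less than half remains, and the visit comes later after the last dose than a completer's does (35 against 28 days). No section gives a time to rebound, and the tocilizumab observation concerns a receptor blocker.

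Finally, some recording already exists: Section 4 documents each administration, Section 11 records reasons for withdrawal, and Section 10 provides for pregnancy and SAE follow-up reports. These do not supply week 52 visits.

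**Conclusion.** The point holds in limited form. Section 11 mixes stopping the drug with leaving the study, and for patients handled under it the only described follow-up is a voluntary visit 7 days after the drug stops. This goes beyond missing detail, because a stated rule can cut follow-up short in a subset that is probably not random, while the primary outcome, the one-year survival outcome and the analysis principle all need data to week 52.

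For each affected patient the loss could be large: on average 25 to 29 of 52 weeks, depending on how the stop is dated and assuming evenly spread stops. The number of such patients rests on rates borrowed from other settings; it is probably small and may be zero. The documents do not support a claim that all drug stops end participation, or that a rebound would necessarily be missed. In a pilot with 10 patients per Part A arm, the change is still worth making, because lost follow-up may not be recoverable later.

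**What to change.** Reconcile Section 11 with the outcomes in Section 5 and the intention-to-treat statement in Section 7, and link the Section 9 rules to it.

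1. State that stopping study drug, or an investigator's decision to withdraw a patient from treatment (including for non-adherence), does not by itself end study follow-up. These patients stay on the non-invasive Table 3 assessments to week 52 unless they withdraw consent: AEs, safety laboratory, eGFR, protein/creatinine ratio, DSA at weeks 12 and 52, and graft and patient status.
2. Make the 7-day visit an additional visit that does not replace the week 52 EOS visit, and define the date from which the 7 days run.
3. Record drug stop and consent withdrawal as separate CRF events, and report the number observed per arm for each endpoint.

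The cost is one amendment and continued visits for a few patients, using assessments already scheduled. It adds no biopsies and leaves the sample size and the week 52 end date unchanged. Biopsies that these patients miss are not recovered. No dose or clinical stopping rule is proposed.

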#### *Premature termination of the study*

The sponsor has the right to close this study at any time. The IEC and the competent regulatory authority must be informed within 15 days of early termination.

The trial or single dose steps will be terminated prematurely in the following cases:

- If adverse events occur which are so serious that the risk-benefit ratio is not acceptable.
- If the number of dropouts is so high that proper completion of the trial cannot realistically be expected.

## **12. ETHICAL ISSUES**

The study will be conducted in accordance with the principles of the Declaration of Helsinki 2008. Ethical committee approval will be obtained for all aspects of the study. All study participants will be asked to sign the informed consent to participate in the study (patient insurance included).

## **13. REGULATORY REQUIREMENTS**

We will adhere to all the trial-related requirements, Good Clinical Practice (GCP) requirements (ICH GCP), Good Laboratory Practice (GLP) and the applicable regulatory requirements.

#### **14. PERIODIC MONITORING**

The designated monitor ([name], Department of Clinical Pharmacology, Medical University Vienna; [contact]) will contact and visit the investigator regularly and will be allowed to have access to all source documents needed to verify the entries in the CRFs and other protocol-related documents provided that subject confidentiality is maintained in agreement with local regulations. It will be the monitor's responsibility to inspect the CRFs at regular intervals according to the monitoring plan throughout the study, to verify the adherence to the protocol and the completeness, consistency and accuracy of the data being entered on them. The monitoring standards require full verification for the presence of informed consent, adherence to the inclusion/exclusion criteria, documentation of SAEs and the recording of the main efficacy, safety, and tolerability endpoints. The monitor will be working according to SOPs and will provide a monitoring report after each visit. The investigator will resolve discrepancies of data. Source data will be checked by the monitor (which means 100% SDV).

